7.6.3 CASIC instructions for completing surveys at a later date

When exiting and resuming an incomplete survey perform the following:

CASIC Online:

1. Simply exit survey using upper right hand corner exit button on pop-up survey window
2. Email [name] to let her know of incomplete assessment and plans to complete or destroy
3. When resuming, click “Start assessment” and enter PPT ID as usual
4. You will be prompted to resume baseline survey, select this option
5. Complete survey as usual

CASIC Remote:

When managing an incomplete survey on CASIC Remote, the RA can select either option outlined below.

CASIC Remote surveys that are incomplete and uploaded to the server using the “upload data” button in the “synchronize subject data” tab cannot be resumed using CASIC Remote. They can only be resumed using CASIC Online, as the data no longer “lives” on the local drive after synchronization. You may resume a survey on CASIC Remote using the instructions below only if the survey data is not synchronized after exiting the survey. However, it is best practice to synchronize the subject data, incomplete and otherwise, at the end of each day. It is likely that these computers will be used for other survey administration during the timeframe that the incomplete survey remains outstanding. It is not possible to leave only the incomplete survey on the local drive and upload the other completed surveys, and it poses a risk of lost study data if surveys are not uploaded to the server in a timely manner, so it is best to upload the incomplete survey and resume using CASIC Online.

This may be less convenient for on-site administration, but since the RA will be working with the participant to re-schedule a time, they should take into account that they will need internet access to resume the survey. For this reason, it may be useful to complete the surveys by phone. In situations in which there are no other surveys on CASIC Remote on the computer in question and there is a reasonably short time period between first administration and completion of the incomplete survey, it may be appropriate to leave the study data from the incomplete survey on the local drive and resume and complete the survey using CASIC Remote.

Option 1: Synchronize subject data and resume survey using CASIC Online:

1. Simply exit survey using upper right hand corner exit button on pop-up survey window
2. Email [name] to let her know of incomplete assessment and plans to complete or destroy
3. Navigate to the “Synchronize subject data” tab on the left hand navigation panel, select “Upload only” to upload the incomplete survey to the host
4. When resuming the survey using CASIC Online, click “Start assessment” and enter ppt ID as usual
5. You will be prompted to resume baseline survey, select this option
6. Complete survey as usual

Option 2: Leave subject data on the local drive and resume survey using CASIC Remote:

1. Simply exit survey using upper right hand corner exit button on pop-up survey window
2. Email [name] to let her know of incomplete assessment and plans to complete or destroy
3. Do not synchronize subject data
4. When resuming the survey using CASIC Remote, click “Start assessment” and enter ppt ID as usual
5. You will be prompted to resume baseline survey, select this option
6. Complete survey as usual

7.6.4 Survey piloting procedures

Research assistants and any staff involved in survey administration should practice administering the surveys before completing with study participants. Piloting surveys will allow for feedback on improving study forms and surveys, and facilitate streamlined administration with initial participants.

- First, pilot survey on 1-2 colleagues to become familiar with the study format, questions, and response options.
- Practice using CASIC to enter practice study data.
- Second, pilot the study with 1-2 food pantry clients.
 - Use incentive gift cards to compensate clients for their time (1 - \$15 gift card per survey)
 - Clients do NOT need to be consented for completing a pilot survey
 - Explain to clients that responses to pilot surveys will not be saved, and the client is free to answer survey questions with real or made-up responses

CASIC is programmed with participant ID numbers that have been identified for use in piloting and training purposes. Use these ID numbers when piloting surveys:

Site	Practice Participant ID Numbers
UCSF / FANO	10 - 29
ACCFB	30 - 49
GCFB	50 - 69
HFB	70 - 89

7.7 Health Care Utilization Analysis

This section contains information and processes specific to the Health Care Utilization (HCU) plan, including communicating with health care providers about the study and health care utilization data requests. A table at the end of this section identifies the different packets used when communicating with providers.

The HCUA is a critical component of the FAITH-DM study. The analysis will provide important information on how participating in the intervention may impact the ways in which a patient utilizes health care services for primary care and diabetes management.

Collection of health care utilization data from providers follows this format: HCU surveys are sent to providers two times over the course of the study: once at T6 for the entire previous 12 month period for both the control and intervention groups, and once at T12 for the previous 6 month period for the intervention group only.

7.7.1 HCUA Roles and Responsibilities

Site research assistants (RAs):

- Track primary care provider (PCP) information for study participants (at T0, T6, and T12) and enter data into MS Access database
- Communicate with PCPs regarding study activities by sending pre-drafted letters and HCU documents per the HCUA plan (see **Appendix Y – Health Care Utilization Provider Letters [1-8]** for all HCU Provider Letters)
- Track PCP completion of HCU surveys and provide follow-up and support as needed
- Compile completed surveys and ensure that documentation is de-identified before sending in batches to the Urban Institute
- Submit and track quarterly payments to clinic partners for data extraction and survey completion fees (per food bank – clinic MOU agreements)

Urban Institute:

- Provide technical assistance to site RAs in communicating HCUA to partner clinics and supporting clinics to complete HCU surveys per study protocols
- Communicate with site RAs to troubleshoot unanticipated challenges relative to completing provider surveys (e.g., participant uses a small, family practice for care which does not have a food bank MOU)
- Work with RAs to revise HCUA processes as needed at the site or clinic level to streamline acquisition of utilization data
- Develop and refine all HCU documents and surveys as needed
- Complete all data entry from submitted provider surveys and documents
- In the event site RAs submit de-identified copies of medical records, Urban Institute will complete data extraction and data entry for use in HCUA
- Manage all HCU-related data and conduct final data analyses

All RAs will be provided with contact information for the appropriate research personnel at the Urban Institute so that they can obtain assistance with any questions or issues that arise during the Health Care Utilization component of the study.

7.7.2 HCUA Activities at Baseline (T0)

The following sections outline HCUA activities that take place when a new participant enrolls in the study.

At enrollment, all participants will be asked to provide the name of their current primary care provider (individual provider and/or practice/clinic site) and to provide consent for communication with provider, including release of medical record information (see **section 5.3** for discussion of consent and HIPAA procedures, and **Appendix AO** for the Medical Records Release Template). The site personnel will request as much contact information for the provider as possible (phone number, address, or nearest cross streets the participant can identify). The RA may need to research and complete the provider contact information if the participant is unable to provide full contact information at the time of enrollment.

If the participant declines to provide consent for the release of medical records from the current provider, this should be documented and entered into the MS Access database. No further action to request information from the provider can be taken regarding release of medical record information. However, when a participant provides informed consent to enroll in the study, study staff does receive participant permission to contact the participant's care provider to inform provider of the participant's entry into the study.

7.7.2.1 Intervention group participants with an existing primary care provider

For intervention group participants who have a PCP, study staff will assemble a baseline provider communication packet that will include:

- Provider Letter (*HCU Letter 1 - T0 Current Pt INT*)
- Copy of the participant's signed HIPAA authorization form

This baseline letter provides background information on FAITH-DM, informs the provider that the participant has enrolled in FAITH-DM, identifies the participant's group assignment, discloses screening results (only for participants assigned to the intervention group), describes the HCUA process, and informs the provider that a care utilization survey will be sent at the participant's 6- and 12-month mark in the study. No action is requested of the provider at baseline.

The provider communication packet should be generated and sent (by fax or mail) within two weeks of the participant's enrollment in the study. A description of how the site can maintain a HIPAA compliant fax is contained in **section 3.2.1**.

7.7.2.2 Intervention group participants without a primary care provider

When the intervention participant does not have an existing source of primary care, he or she will receive an active referral per the process outlined in **section 3.2.1**. A modified baseline provider communication packet will be assembled and includes:

- Provider Letter (*HCU Letter 2 - T0 Newly Referred Pt INT*)
- Copy of the participant's signed HIPAA authorization form

The RA will need to verify the primary care provider information at the six-month participant survey (and is prompted by CASIC to do so).

The provider communication packet should be generated and sent (by fax or mail) within two weeks of the participant's enrollment in the study.

7.7.2.3 Waitlist control group participants with an existing primary care provider

For participants assigned to the waitlist control group and who state they have an existing primary care provider, the following communication packet will be sent to the provider:

- Provider Letter (*HCU Letter 3 - T0 Current Pt CONT*)
- Copy of the participant's signed HIPAA authorization form

The provider communication packet should be generated and sent (by fax or mail) within two weeks of the participant's enrollment in the study.

7.7.2.4 Waitlist control group participants without a primary care provider

If a waitlist control participant does not have an existing source of primary care, he or she will receive a provider resource handout (passive referral) per **section 3.2.1**.

No provider communication packet is required for this group at T0.

If the participant states they do not have a provider now, but they did receive primary health care services in the last six months, then the RA should complete the steps listed above for sending a communication packet (*HCU Letter 3 - T0 Current Pt CONT*) to their previous provider and offer a resource handout for the participant to establish care with a new provider. Contact information for the previous provider should be stored in Access to use when sending out HCU surveys at T6.

The RA will need to repeat the request for whether there is a current primary care provider at the point at which the participant becomes eligible to enroll in the intervention at six months (the 6-month participant survey includes a prompt in CASIC for this inquiry).

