7.7.3.2 Study participants without provider at T0 but have provider at T6

For participants who did not have a provider at baseline (T0), but do identify having a provider at the six-month mark (T6), site staff will send the same T6 packet identified above to the participant’s new provider.

The T6 provider packet for these participants includes:

- Provider Letter (*HCU Letter 4 - T6 Current Pt*)
- Copy of signed HIPAA form
- Copy of signed Medical Records Release Form
- HCUS (**Appendix Z**)

The RA should follow the process outlined above for completing portions of the HCUS and sending the packet to providers.

7.7.3.3 Study participants without provider at T0 and who still do not have a provider at T6

For participants who did not have a provider at baseline (T0), and still do not identify having a provider at the six-month mark (T6), site staff will generate an active referral to a partner clinic per the process outlined in **section 3.2.1**.

In addition to the referral for care, site staff will send a modified T6 packet to the participant's new provider.

The T6 provider packet for these participants includes:

- Newly Referred Patient T6 Letter (*HCU Letter 5 - T6 Newly Referred Pt*)
- Copy of signed HIPAA form
- Copy of signed Medical Records Release Form
- HCUS (**Appendix Z**) – for use in the event the provider does have records for this participant

The RA should follow the process outlined above for completing portions of the HCUS and sending the packet to providers.

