7.7.3.4 If a participant has switched providers between T0 and T6

It is possible that a participant may have switched primary care providers during the study intervention period. This could occur for several reasons: the participant may have moved and the prior provider location was no longer be convenient; the provider may have closed or changed the conditions under which it sees patients (e.g., the provider is no longer on the panel for the participant's insurance plan); the participant may have had a change in insurance or coverage status that affects his or her provider options; or the participant has decided to change for other reasons. It is important that the RA re-verify the primary care provider information for all participants at the six month survey point and note where any changes may have been made.

If there is more than one provider during the six-month period, then requests for records should be made to all primary care providers the participant has identified. Each provider will receive a T6 provider packet; however, the new provider should receive a modified version of the T6 letter that does not assume any prior communication with that provider (see: *HCU Letter 5 - T6 Newly Referred Pt*). The RA should make a note in the MS Access database that provider data is being requested from multiple providers. This information should be recorded on all survey forms for that participant

once they have been returned and logged into the database so that the analysis team is aware that two or more surveys will be entered for that period and special attention can be paid to reconciling the information for that participant.

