13.5.1 Participant and provider data collection process

Self-reported data on the use of selected health care services will be collected from all participants in the survey administered at enrollment (T0), after six months in the study (T6), and again six months after completion of the initial intervention or waitlist period (T12) (see **section 7.6** for a general description). In each survey, the study participant will be asked to report on health care utilization in the prior six months. At enrollment (T0), the participant will also be asked to provide consent for the release of medical record information from their current primary care provider during the enrollment process.

If the participant reports he or she does not currently have a primary care provider, the participant will be given an active referral if part of the treatment group and offered a provider resource sheet if part of the waitlist control group.

After the participant has been in the study for six months, the site RA will send a health care utilization survey to the primary care provider the participant identifies at enrollment. The site RA will also ask if there has been any change in primary care provider during the prior six months and will send additional surveys as appropriate. The provider survey will be accompanied by (see **Appendix Y**) a brief explanation of the survey and contact information for any questions or assistance needed in completing the request, as well as a copy of the signed HIPAA and medical records release authorization.

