The T6 provider survey will query dates of service for primary care visits made in the past 12 months for each participant (the six month period prior to enrollment, and the following six month period during the intervention or waitlist window), as well as the primary associated CPT codes and up to four ICD-9/ICD-10 diagnosis codes. The provider survey is not restricted to services provided for diabetes or diabetes complications since it may be difficult to discern whether a particular condition is associated with or affected by diabetes. The provider survey will also ask for dates of any scheduled but missed appointments. Providers will be asked to list the dates of service, primary procedure codes and diagnosis codes for any emergency department visits or inpatient hospital admissions for which they have records. Although the records of these services may be less complete than those delivered directly by the provider practice/clinic, it is standard practice for hospitals to forward discharge summaries if a provider is identified at the time of admission and we will obtain this information whenever possible.

At T12, provider surveys will be sent only to those providers who have cared for a study participant originally enrolled in the intervention group. The information collected will be identical to that requested at T6, but will focus on utilization during the intervening six-month period. Providers who cared for a study participant originally enrolled in the waitlist group will not receive a survey for that participant.

See **section 7.7** for additional details on the processes for communicating with providers and obtaining completed health care utilization surveys.

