13.5.4 Statistical analyses

For each of the outcomes from the utilization analysis we would assess the impact of the intervention using the following specification:

$$Y_i = \beta_0 + \beta_{1,i}T + \beta_{2,i}Post + \beta_{3,i}T * Post + \epsilon_i$$

Where Y_i is the given outcome variable, T_i is an indicator for being assigned to treatment, $Post$ is an indicator that the observation is from the post intervention time period, and ϵ_i is the error term. The impact of the intervention is measured by β_3 which measures the intent to treat effect – or the change in the outcome of interest for the treatment group compared to the change in the outcome of interest for the wait-list group. Since randomization is at the individual-level, HuberWhite standard errors will be used.

Loss to follow-up

We intend to follow the same procedures for loss to follow-up as specified in the analysis of the primary study outcome (HbA1c). We will conduct a formal missingness investigation to determine if the attrition rate differed between intervention and waitlist groups. If treatment status is found not to significantly affect attrition at the 5 percent significance level, then all estimation will proceed without

any adjustment for attrition. If attrition is found to be related to treatment status, we postulate that attrition will be higher for the control group, and will employ Lee bounds to obtain bounds on our treatment estimates which are robust to this attrition. Multiple imputation for missing outcome data will also be explored as sensitivity analyses.

Subgroup analyses

While the study is randomizing within sites, we also plan to conduct subgroup sensitivity analyses by both adjusting for site and examining changes within site to determine differential effectiveness by location. Site-specific differences will be shared with the food pantries, but only reported publicly in manuscripts if found to be significantly different.

Other planned subgroup analyses (as specified in our hypotheses) are by baseline glycemic control (>9%) and food security status.

14 Quality Control Procedures

Data integrity and study credibility depend on factors such as:

- Ensuring adherence to the protocol
- Obtaining complete follow-up information on all participants enrolled
- Using quality control measures to establish and maintain high standards for data quality

Quality control procedures for point-of-care testing is described in **section 7**.

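### For participants with no current provider, records from a provider seen before enrollment are sought in the control arm only, so the provider-record baseline is ascertained differently by arm

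*Combined protocol and SAP*

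**What the plan says.** **Control arm, no current provider (7.7.2.4).** The default is a resource handout and no provider packet. There is an exception: "If the participant states they do not have a provider now, but they did receive primary health care services in the last six months", the research assistant sends the control-arm baseline letter to the previous provider. The section then says: "Contact information for the previous provider should be stored in Access to use when sending out HCU surveys at T6".

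**Intervention arm, no current provider (7.7.2.2).** "When the intervention participant does not have an existing source of primary care, he or she will receive an active referral". A letter goes to the referred clinic, and provider details are checked again at the six-month survey. Nothing is said about a provider seen before enrollment.

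**At T6, both arms.** For someone without a provider at T0 who has one at T6, "site staff will send the same T6 packet identified above to the participant’s new provider" (7.7.3.2). The rule for several providers reads: "If there is more than one provider during the six-month period, then requests for records should be made to all primary care providers" (7.7.3.4, on switches between T0 and T6). Section 13.5.1 has the site "ask if there has been any change in primary care provider during the prior six months".

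**Use of the data.** Section 13.5.1 says: "The T6 provider survey will query dates of service for primary care visits made in the past 12 months for each participant", so one form supplies both the six months before enrollment and the six months after. The effect in 13.5.4 is "the change in the outcome of interest for the treatment group compared to the change in the outcome of interest for the wait-list group". The primary utilization indicator (13.5.2) is change in primary care use, taken from self-report and, where available, provider reports. An increase is hypothesized. For emergency and inpatient use the hypothesis is a possible trend toward reduction.

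**The concern.** A difference-in-differences estimate needs the baseline to be measured the same way in both arms. Here, whether a previous provider is asked for records depends on allocation. Randomization gives no protection, because the difference arises after assignment, in how the data are collected.

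A clinic first attended after enrollment can return a valid 12-month form that shows nothing before enrollment. In the control arm, a second form from the previous provider would fill that gap. In the intervention arm no such form is requested. At stake is the provider-record version of the primary utilization indicator, and its value as a check on self-report.

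**Working it through.** The plan states no figure on this point, so there is none to reproduce. The check has two parts: whether the asymmetry is real, and what it does to the estimate.

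**1. Is the gap closed elsewhere?**

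| Place | Previous-provider step, intervention arm |
|---|---|
| 3.2.1 | None: written information and active referral |
| 7.7.2.2 | None |
| 7.7.3.2, 7.7.3.3 | None: the survey goes to the new or newly referred provider |
| 7.7.3.4 | Covers more than one provider between T0 and T6, not one left before T0 |
| 7.7.8 table | None |
| 13.5.1 | Asks about change in the prior six months, that is, since enrollment |

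The 7.7.8 table omits the step for controls as well, so control-arm capture may be incomplete in practice.

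**2. Direction, if an absent record is read as zero.** The effect is β3 = (I_post − I_pre) − (C_post − C_pre), where I is intervention and C is control. Let:

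- q = share with no provider at T0
- s = share of those seen by a previous provider in the prior six months
- v = their mean visits in that period
- c = share of those visits captured in controls
- w = share recovered in the intervention arm because the person is back with that provider by T6

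Recorded I_pre is too low by q·s·v·(1 − w), and recorded C_pre by q·s·v·(1 − c). With no true effect, the bias in β3 is q·s·v·(c − w). It is positive whenever controls are captured more fully.

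**3. Size.** The documents give none of q, s, v, c or w. All values below are assumptions, with c = 1.

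| Case | q | s | v | Bias, w = 0 | Bias, w = 0.5 |
|---|---|---|---|---|---|
| Low | 5% | 10% | 1 | +0.005 | +0.0025 |
| Middle | 15% | 30% | 1.5 | +0.0675 | +0.034 |
| High | 30% | 50% | 2 | +0.30 | +0.15 |

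With c = 0.7 and w = 0, the middle case is 0.0675 × 0.7 = +0.047.

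If intervention participants also make visits to the old provider after T0 that go unrecorded, the bias shrinks. Where those are half as many as the missed baseline visits, the middle case is 0.0675 × 0.5 = +0.034. Where they are equal it is 0, and beyond that the sign reverses.

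**4. Emergency visits.** Take q = 15%, s = 30% and 0.5 missed visits each. The shift is 0.15 × 0.30 × 0.5 = +0.0225. An assumed true change of −0.10 would read −0.10 + 0.0225 = −0.0775, so part of the reduction is hidden.

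**5. Scale against sampling error.** The provider-data goals in 13.5.3 are 80% and 70% of 300, or 240 and 210 participants. With an assumed visit SD of 2, SE = 2 × √[2(1 − ρ)(1/240 + 1/210)], where ρ is the pre-post correlation. This is 0.267 at ρ = 0 and 0.189 at ρ = 0.5. With w = 0, the middle case is 0.25 to 0.36 SE, the high case is 1.1 to 1.6 SE, and the low case is negligible.

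**6. If an absent record is read as missing.** The formula in step 2 no longer applies. Controls in this subgroup contribute a baseline and comparable intervention participants do not. That is selection by arm, and its direction cannot be given from the documents.

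**The case against.** The case on the other side is substantial, and most of it stands as a limit on the claim.

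- **Returners.** Both arms are asked about their provider at T6. An intervention participant who has gone back to the old clinic names it, and the 12-month look-back recovers the baseline visits. The draft clinic agreement (Appendix O) also foresees referral to a clinic where the client is already established. It would therefore be wrong to infer that the same person always contributes real baseline visits in one arm and zero in the other.
- **Zero is not stated.** A provider with no record of the patient returns the face sheet (7.7.3.1), unanswered requests can be classed as nonresponse (7.7.5), and 13.5.4 has procedures for loss to follow-up. This stands in part. None of these says how to treat a valid form from a new clinic that is blank before enrollment.
- **Self-report.** It is collected identically in both arms at T0, T6 and T12 (13.5.1) and is a named source for the primary indicator. This stands in full.
- **Subgroup size.** Section 13.5.3 reports that most people in the pilot had a provider. Those without one are also the least likely to yield any provider record. This stands.
- **Unseen material.** The Appendix AP flowcharts and the attached letters and surveys are not reproduced in the text available and could contain a prompt. That cannot be excluded, but the written sections would still need to agree with it.

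A reader might also infer a badly inflated test. Null simulations at biases of +0.03, +0.15 and +0.30 visits (gamma-Poisson counts, mean 1.5 visits per six months, no returners) gave false-positive rates of about 6%, 15% and 41% with a person-level variance. With unclustered errors and an assumed gamma shape of 1, they gave 0.3%, 2.3% and 13%. Section 13.5.4 names Huber-White errors and does not mention clustering by person, and the shares are assumed. The documents therefore support no particular error rate.

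**Conclusion.** The procedures differ by arm as written, and nothing in the text available corrects this. Provider-record baselines are therefore ascertained differently for participants with no current provider who had recent primary care, apart from intervention participants who have returned to that provider by T6.

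It is tempting to conclude that the trial's utilization effect is overstated. The documents do not support that. The upward shift needs absent records to be read as zero, it concerns provider records only, and for emergency and inpatient use it works against the hypothesis. Its amount, up to +0.30 visits per person, rests wholly on assumed shares and may be trivial. The arm difference itself is certain on the text. This is worth correcting because the remedy is cheap, not because harm has been shown.

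**What to change.** 1. Add to 7.7.2.2 what 7.7.2.4 already does: ask about primary care in the last six months, send the previous provider a notice packet, store the contact, and send that provider the T6 survey. Show the step for both arms in the 7.7.8 table.
2. State in 13.5.4 when an absent pre-enrollment record counts as zero visits and when it counts as missing.
3. For intervention participants already enrolled without this step, ask at T6 about any provider seen in the six months before enrollment, and send the survey there.
4. Add a sensitivity analysis that excludes records obtained only through a previous-provider request in either arm, and report provider-record results beside self-report.

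**Cost.** A wording change and a few extra surveys at $20 each (7.7.6). The release dates in section 5.5 already reach back six months before enrollment. The drawback is that the catch-up question relies on longer recall in one arm than the question put to controls at T0, which is why step 4 is needed. With equal capture in both arms (c = w), the bias in step 2 of the working is zero.
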